6.4 STUDY INTERVENTION/EXPERIMENTAL MANIPULATION ADHERENCE

For participants in the HIWL or HIWL + CGM interventions, participation and engagement will be monitored through the Carium platform on a regular basis. At the end of each week of participation, a summary assessment of participant engagement levels will be generated from the platform. Individuals who show unexplained drop offs in participation levels will have follow up outreach to assess key factors that might be affecting engagement.

For participants in the control intervention, participation and engagement will be monitored during participation in the group-based DSME. There will be a regular review of food diaries and tailored information provided to the participants to help guide plan implementation. Participants who are showing signs of lower or decreased engagement will be engaged by the study team to see what can be done to maintain/improve engagement.

6.5 CONCOMITANT THERAPY

6.5.1 RESCUE THERAPY

Medication adjustment: For participants in the data-assisted HIWL arms, the medical weight loss team will make medication adjustments at the beginning of the intervention, at any subsequent clinic visit or

encounter where the participant reports symptoms of hypoglycemia with corresponding low blood glucose readings, or at quarterly assessments of HbA1c. For participants in the DSME intervention, [name] will meet weekly with the diabetes education interventionist to review participant blood glucose logs and make adjustments in medication dosing. Participants will be asked to self-monitor BG values at least twice daily (fasting and pre-dinner meal), not including additional measures if they are experiencing signs/symptoms of hypoglycemia. At each clinic visit, we will review the average values and ascertain episodes of hypoglycemia, defined as glucose levels less than 70 mg/dL. If the participant reports an episode of severe hypoglycemia (hypoglycemia resulting in a loss of consciousness or inability to self-treat) or symptomatic hypoglycemia on multiple occasions to a non-clinical staff member, one of the study clinicians will be notified to make adjustments in medications within 24 hours per the protocol (Table 4). Medication can be discontinued if the lowest dose available is being prescribed and the average BG \leq 140 or HbA1c $<$ 6.5%. Once total insulin dose is below 20 units daily with adequate control, the participant will be transitioned to an oral medication regimen (i.e., non-insulin).

Table 4. Medication Dose Adjustment Plan			
Event	Action	Follow up	Desired outcome
Initiating weight loss intervention	Reduce meds by up to 50% and/or discontinue all oral hypoglycemic	1 week	No hypoglycemic events and average BG less than or equal to baseline A1c
One episode of severe hypoglycemia or symptomatic hypoglycemia 2 times or more per week	Reduce meds by 50-100%	1 week	No hypoglycemic events
14-day average BG $<$ 126	Reduce meds by 25-50%	2 weeks	Average BG \leq 140
14-day average BG $>$ 140 in absence of hypoglycemia	Increase meds by 25%	2 weeks	Average BG \leq 140 and no hypoglycemia
HbA1c $>$ 7% at quarterly assessment	Increase meds by 25% or add new class	2 weeks	Average BG \leq 154 and no hypoglycemia

7 STUDY INTERVENTION/EXPERIMENTAL MANIPULATION DISCONTINUATION AND PARTICIPANT DISCONTINUATION/WITHDRAWAL

7.1 DISCONTINUATION OF STUDY INTERVENTION/EXPERIMENTAL MANIPULATION

When a subject discontinues from HIWL, HIWL + CGM, or Control groups, but not from the study, remaining study procedures will be completed as indicated by the study protocol. If a clinically significant finding is identified (including, but not limited to changes from baseline) after enrollment, the investigator or qualified designee will determine if any change in participant management is needed. Any new clinically relevant finding will be reported as an adverse event (AE).

The data to be collected at the time of study intervention discontinuation will include the following:

- The reason(s) for discontinuing the participant from the intervention, and methods for determining the need to discontinue
- If the participant is due to complete assessments within 2 weeks of being discontinued from the study intervention, those assessments will be administered at the time of discontinuation; if the next scheduled assessments are more than 2 weeks from the discontinuation date, the discontinued participant will wait for the next scheduled assessment. Thereafter, the participant will be included in all future scheduled assessments, even though not participating in the intervention.

7.2 PARTICIPANT DISCONTINUATION/WITHDRAWAL FROM THE STUDY

Participants are free to withdraw from participation in the study at any time upon request.

An investigator may discontinue a participant from the study for the following reasons:

- Initiation of a disqualifying weight loss treatment (e.g., bariatric surgery)
- Lost-to-follow up; unable to contact subject (see **Section 7.3, Lost to Follow-Up**)
- Any event or medical condition or situation occurs such that continued collection of follow-up study data would not be in the best interest of the participant or might require an additional treatment that would confound the interpretation of the study
- The participant meets an exclusion criterion (either newly developed or not previously recognized) that precludes further study participation (e.g., becomes pregnant)

The reason for participant discontinuation or withdrawal from the study will be recorded on the Study Discontinuation Case Report Form (CRF). Subjects who sign the informed consent form and are randomized but do not receive the study intervention may be replaced. Subjects who sign the informed consent form, and are randomized and receive the study intervention, and subsequently withdraw, or are discontinued from the study, will not be replaced.

7.3 LOST TO FOLLOW-UP

A participant will be considered lost to follow-up if he or she fails to return for 3 consecutive scheduled visits and study staff are unable to contact the participant after at least 3 attempts.

The following actions must be taken if a participant fails to return to the clinic for a required study visit:

- The site will attempt to contact the participant, reschedule the missed visit within 5 business days, counsel the participant on the importance of maintaining the assigned visit schedule and ascertain if the participant wishes to and/or should continue in the study.
- Before a participant is deemed lost to follow-up, the investigator or designee will make every effort to regain contact with the participant (where possible, 3 telephone calls and, if necessary, a certified letter to the participant's last known mailing address or local equivalent methods). These contact attempts will be documented in the participant's study file.
- Should the participant continue to be unreachable, he or she will be considered to have withdrawn from the study with a primary reason of lost to follow-up

8 STUDY ASSESSMENTS AND PROCEDURES

8.1 ENDPOINT AND OTHER NON-SAFETY ASSESSMENTS

All measures will be assessed at baseline and every 3 months thereafter (unless a different schedule is specified below). The primary outcome (change in body weight) will be assessed as weight at 12 months – weight at baseline.

Weight: Weight and height will be measured in light indoor clothes without shoes using standard procedures. Weight measurements will be taken to the nearest 0.1kg by a high-quality digital scale. Scales will be calibrated annually by the Bureau of Weights and Standards and quarterly by trained study personnel using standard weights. Height will be measured using a standard wall-mounted stadiometer. Study personnel will be trained and certified to follow measurement procedures according to study protocol. Percent weight loss will be calculated based on baseline weight obtained at the first in-person screening visit.

Glycemic control: Serum HbA1c measurements will be drawn quarterly on all participants. Assessment of glycemic control will be done in the context of anti-diabetes medication usage. Documentation of medications will be obtained electronically from all available sources (e.g., EHR, pharmacy) and by physical review of medicines using the “brown bag” method. Participants will be requested to bring all of their medication to the clinic for review. Research assistants will reconcile medication regimens from the electronic record and those presented by the patient. Medicines will be described as any prescription or non-prescription substance they take on a regular basis including tablets, liquids, inhalers, creams and ointments. Continuous glucose monitoring (CGM) with sub-dermal sensors will be used as a secondary measure of glycemic control for all participants. CGM provides information beyond what traditional finger stick blood glucose testing affords. CGM provides measurements of interstitial blood glucose (BG) at 1- 15 minute intervals and correlates well with capillary blood glucose measurements. Collection of continuous glucose values allows immediate recognition of current BG and prediction of trajectory of BG; preventing hypoglycemia. We will utilize the FreeStyle Libre, which is one of the most frequently used CGM in the world as a result of both its accuracy and simplicity of use. Sensors are placed on the upper arm using a painless spring loaded injector. BG recordings are available within an hour and the device will record BG every 15 minute minutes without a need for calibrations for 2 weeks. CGM related outcomes that we will assess at baseline and 12 months include time in range, episodes of hypoglycemia, glucose variability, and average glucose. For individuals in the HIWL + CGM arm of the trial, data from the CGM they are using in the intervention will be used for these outcomes.

Diabetes remission: Diabetes remission status will be assessed at 12 months as a secondary outcome for this study. At the time of assessment, if the participant has achieved an HbA1c of 5.7-6.4% without the use of anti-diabetes medications, the participant will be classified as being in partial remission. If the participant has achieved an HbA1c of <5.7% without any medications, the participant will be classified as being in complete remission. The sum of these two outcomes will comprise the outcome of any remission (partial + complete).

Demographics: Demographic information including sex, race/ethnicity, and date of birth (age) will be captured at the first screening visit during verification of eligibility. Medical history including date of

diabetes diagnosis (duration of diabetes) and co-morbid conditions will be captured by interview and verification from the medical record when available.

Dietary intake: To assess **dietary intake**, we will use NCI's automated, self-administered 24-hour dietary recall, the Automated Self-Administered 24-hour (**ASA24**®) dietary assessment tool (version: ASA24-2018). The ASA24-2018 will be completed on three, non-consecutive days (including one weekend day) at baseline (pre-randomization), and again at months 3, 6, and 12. The ASA24-2018 is available for use on computers and mobile devices. At the baseline visit, participants will complete one ASA24 assisted by a research staff member. They will then be asked to complete a second and third ASA24 during run-in, on their own, as a part of the baseline assessment. During office visits at each relevant follow-up time point (3, 6 and 12 months), participants will again complete the ASA24. Following each of these visits, a staff member will contact participants within six days (on a randomly selected day) to inform them to complete 2 additional dietary recalls and will offer to conduct the recall over the phone if needed (the ASA24 performs equally well as a self- or interviewer- administered questionnaire).^{23,24} Follow-up reminder calls will be made to encourage completion of the recalls if not completed within 24-hours following a contact. Using the ASA24 data from each time point (baseline, 3, 6, and 12 months), specific outcomes of interest will include: **total daily energy intake** (kcal; averaged across 3 days), **macronutrient composition** of diet (%Carbohydrate/Fat/Protein; averaged across 3 days), **number of eating episodes** per day, and **Healthy Eating Index (HEI)-2015** score (a validated summary measure of dietary quality, rated on a 100-point scale,^{25,26} which is sensitive to change with dietary intervention^{26,27}, and can be calculated using publicly-available SAS code from the ASA24 website).

Physical activity: We will use pedometers to assess objective physical activity (PA) – operationalized as **daily step counts** – at baseline, 3, 6, and 12 months. Although accelerometry is the gold standard for objective PA measurement,²⁸ pedometers have 99.8% step count accuracy, particularly when worn at the hip.^{29,30} For our study, participants will be fitted with a pedometer and asked to wear it for all waking hours (except while bathing or water activities) over their right hip for 7 consecutive days at each relevant time point in follow-up. At the end of the 7th day, participants will open the unit, record the final step count, and return the pedometer to WFSOM via a pre-stamped mail envelope. **Self-report:** In order to compare our results with the extant literature that has used self-reported PA outcomes, we will also include the short form of the IPAC, a self-report instrument with good reliability (Spearman's rho=0.8) and criterion validity comparable to other self-report instruments.³¹

Diabetes medication class/dose: All medications will be assessed quarterly as previously described. Variables of interest include medication name, total dose, and class of medication at baseline and longitudinal changes during the trial follow up.

Healthcare utilization and quality of life: To capture differences in quality of life associated with the intervention arm, we will use EuroQol's EQ-5D-5L instrument as the quality measure³². This instrument takes responses to five questions on mobility, self-care, ability to perform usual activities, pain, and anxiety/depression to produce a validated quality score (0 to 1). This instrument will be administered at baseline and at the end of the study (12 months). We anticipate no patient deaths during the study period; as such, we will treat the difference in the quality score at the end of the study period and at baseline as the change in the quality of life year (QALY). For instance, if the quality score is 0.4 at baseline and 0.6 at the study-end, the change in the quality of life will be 0.2 QALYs.

Cost data: There will be two cost categories: *intervention costs* and *healthcare utilization costs*. Intervention costs will cover the costs incurred in the implementation of the intervention. This will include, for the HIWL arm, the provider visits (in-person and telemedicine) associated with the intervention will be assessed in terms of the insurance reimbursement (\$). For intervention services and resources not reimbursed by insurance (meals, software installation, staff time), we will use the micro-costing approach to aggregate the costs. As insurance reimbursement for the same service may vary by insurer, we will use Medicare fee-for-service reimbursement as the standardized rate so as to limit confounding arising from differences in insurer composition across intervention arms (ResDAC 2020). Patient out-of-pocket costs will also be included (e.g., insurance co-payments and deductibles). We will not include any costs relating to the research administration (e.g., staff time for data collection and analysis). For the HIWL+ CGM arm, we will include the cost of continuous glucose monitoring. Healthcare utilization costs will include healthcare services used during the study period but are not part of the interventions: hospitalizations, emergency department visits, outpatient visits, and prescription medications. Costs of these services will be assessed at Medicare rates. We will refer to the sum of the intervention and healthcare utilization costs as the *total costs*. Note that an intervention may lead to higher intervention costs compared to the control arm; however, if an intervention results in higher rates of diabetes remission, then healthcare utilization may be lower for the intervention cohort, compared to the control arm. The total cost captures the net change of the higher intervention and lower utilization costs.

Cost-effectiveness Outcomes: Our main outcome for cost-effectiveness analysis will be diabetes remission. We will compare the relative costs of achieving one additional remission using alternative interventions. As secondary outcomes, we will also examine the cost-effectiveness of (a) one percentage unit reduction in A1c and (b) one additional QALY.

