Study Population:	Participants will be individuals 18 and older who have T2DM diagnosed within the past 6 years with a BMI of 27-50 kg/m ² . Participants must have an HbA1c between 6.5-11.9%. Sample size will be 30 participants per treatment group.
Phase* or Stage:	Phase 4
Description of Sites/Facilities Enrolling Participants:	Wake Forest Baptist Health Weight Management Center (WMC) Wake Forest Baptist Health Diabetes Center (DC)
Description of Study Intervention/Experimental Manipulation:	Participants randomized to the HIWL treatment group will be placed on a meal replacement-based weight loss protocol. Our active intervention will be delivered with the aid of a technology platform that will automate portions of the intervention and assist clinicians in tailoring treatment and responding to participant needs in a “just-in-time” manner that we frame as a “data-assisted approach.”
Study Duration*:	15 months
Participant Duration:	12 months

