4 STUDY DESIGN

4.1 OVERALL DESIGN

This project will determine if a data-assisted, high intensity medical weight loss intervention (HIWL) will lead to significant weight loss and diabetes remission in individuals with a BMI 27-50 kg/m² with T2DM of less than 6 years as compared to a diabetes self-management education intervention (DSME). Complete diabetes remission is considered to be achieved when the patient is not taking any anti-diabetes medication for at least 12 months, and the HbA1c is < 5.7%. Partial remission is achieved when the patient is not taking any anti-diabetes medication and has an HbA1c of 5.7-6.4% for at least 12 months. Using a randomized controlled study design, we will randomly assign 90 participants to HIWL, HIWL + CGM, or DSME. Participants assigned to HIWL will receive a high intensity behavioral weight loss intervention delivered using a digital patient engagement platform. Participants will be prescribed a low calorie dietary plan and a recommended physical activity program designed to produce 15-20% weight loss over 12 months. Those assigned to HIWL + CGM will receive the same intervention as HIWL; in addition we will provide them with CGM to use as part of their remote monitoring on a daily basis. Those assigned to DSME will participate in a comprehensive diabetes education program designed to provide education and skills for optimal diabetes management plus lifestyle modification counseling to produce 5% weight loss over the same timeframe. The primary outcome of weight loss will be assessed at 12 months.

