9 STATISTICAL CONSIDERATIONS

9.1 STATISTICAL HYPOTHESES

1. Test the effectiveness of the combined interventions (data-assisted approach for high intensity medical weight loss) for weight loss in a group of adults with recently diagnosed type 2 diabetes compared to standard of care diabetes self-management education.
H1- The data-assisted approach for HIWL (with or without CGM) will lead to 12% greater weight loss compared to the standard of care DSME.
2. Assess the impact of the data-assisted approach for high intensity medical weight loss on glycemic control outcomes including hemoglobin A1c and diabetes remission rates compared to diabetes self-management education.
H2a- The data-assisted approach for HIWL (with or without CGM) will lead to greater reduction in HbA1c compared to DSME.
H2b- The data-assisted approach for HIWL (with or without CGM) will lead to a greater proportion of participants achieving diabetes remission ($\text{HbA1c} < 6.5\%$) compared to DSME.
3. Explore impacts of adding CGM to the HIWL intervention on time to achieve A1c goals and participant satisfaction.
H3a- The HIWL + CGM approach will achieve A1c goals in a shorter timeframe than HIWL alone.
H3b- Participant satisfaction will be equivalent between the HIWL and HIWL + CGM approaches.
4. Explore differences in healthcare utilization between the treatment groups.
H4- The HIWL groups will have lower healthcare utilization compared to standard of care DSME.

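### Remission is read from drug status at the 12-month visit with no minimum time off medication, so a participant whose drug stopped shortly before week 52 can be counted as in remission

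*Combined protocol and SAP*

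**What the plan says.** Section 8.1 sets the time of assessment: "Diabetes remission status will be assessed at 12 months as a secondary outcome for this study". The partial grade applies as follows: "At the time of assessment, if the participant has achieved an HbA1c of 5.7-6.4% without the use of anti-diabetes medications". The complete grade needs a value below 5.7% without medication. "The sum of these two outcomes will comprise the outcome of any remission (partial + complete"), so in effect any remission is HbA1c below 6.5% off drugs at one visit. Section 8.1 asks for no off-drug interval and no confirmatory value.

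Other sections bear on this:

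- Synopsis (1.1), entry: "Participants must have an HbA1c between 6.5-11.9" per cent. Section 5.1 lists no HbA1c range and admits people with or without medication.
- Section 6.5.1: "Medication can be discontinued if the lowest dose available is being prescribed and the average BG" is at or below 140, or HbA1c is below 6.5%. No earliest or latest time is given.
- Section 4.1 asks for duration. "Complete diabetes remission is considered to be achieved when the patient is not taking any anti-diabetes medication for at least 12 months" and HbA1c is below 5.7%. Partial remission requires a patient "not taking any anti-diabetes medication and has an HbA1c of 5.7-6.4% for at least 12 months".
- Sections 1.1 and 3 print the same HbA1c range, 5.7 to 6.4%, for both grades.
- Section 9.1, H2b: HIWL "will lead to a greater proportion of participants achieving diabetes remission", with HbA1c below 6.5% and no medication condition.

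Remission is also the main cost-effectiveness outcome (8.1).

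**The concern.** The HbA1c level that permits stopping the lowest dose is the level that defines remission, and it is reached on the drug. HbA1c averages glucose over preceding weeks, so a value drawn soon after a stop partly describes the treated period. Because Section 8.1 looks at drug status on one day only, it cannot tell this participant from one who has held that HbA1c unaided for months.

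A second, smaller route concerns people who enter unmedicated. The entry floor meets the remission ceiling, so a move from 6.5% to 6.4% is enough to be called in partial remission.

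At stake are the reported remission rates, H2b, and the denominator of the cost per additional remission. With 30 per arm, two wrong calls move an arm by 2/30 = 6.7 points.

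**Working it through.** **1. The plan's own figure.** Section 9.2 states power above 95% for weight. With 24 evaluable per arm (20% loss), difference 12 and SD 6.8: 12 / (6.8 × √(2/24)) = 6.11, and Φ(6.11 − 1.96) = 99.998%. The claim reproduces and is not affected here. No power is stated for remission.

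**2. Which definition can be applied.** Follow-up is 12 months (4.4). Someone entering at 6.5% or above cannot also have had 5.7 to 6.4% for 12 months by the end, so the partial grade in 4.1 is unreachable in the trial. Its complete grade is open only to someone off drugs from about baseline. Section 8.1 is the rule that can be used, and it drops duration.

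**3. How long a stopped drug still shows.** The documents give no lag, so this is assumed: HbA1c is a 12-week average with linearly declining weights, and untreated HbA1c is 7.0%. If the drug effect D vanished on the day of stopping, a stop s weeks earlier would leave weight ((12 − s)/12)² on the treated period.

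- D = 1.0, s = 1: 7.0 − (11/12)² = 6.16%.
- D = 1.0, s = 4: 7.0 − (8/12)² = 6.56%.
- s = 12: 7.0%.
- The reading stays below 6.5% for 12 × (1 − √0.5) = 3.5 weeks if D = 1.0, and for 12 × (1 − √(0.5/0.6)) = 1.0 week if D = 0.6.

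If the effect instead fades with a 7-day time constant, D = 1.0 gives about 6.06% at one week, 6.43% at four and 6.99% at twelve (the second decimal depends on how days are counted). On these assumptions an off-drug interval of about one quarter removes the artefact.

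**4. How often a late stop matters.** Simulation, all inputs assumed except the triggers and the glucose line:

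- glucose = 140 + 28 × (HbA1c − 6.5), from the pairs 6.5%/140 and 7%/154 in 6.5.1;
- reviews every 14 days, with noise SD 8 mg/dL on the 14-day mean;
- a stop at or below 140 taken with probability 0.25 to 1, and the drug resumed above 140;
- drug effect 0.6 to 1.0 points, HbA1c error SD 0.15.

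Each person may stop once, first possible at a random review. Share off drug with HbA1c below 6.5% at week 52:

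| Untreated HbA1c | Share |
|---|---|
| 6.7% | 6–8% |
| 7.0% | 2–5% |
| 7.3% | 0–2% |

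If the single stop is possible from week 0, the share is 0 to 0.1%, because nearly all stops then come early.

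**5. Unchanged, untreated entrants.** Assumed: true HbA1c = 5.6 + a gamma variable, with mean 7.2, 7.6 or 8.0 and SD 1.0, 1.2 or 1.4 respectively; entry on a measured 6.5 to 11.9%; independent error SD 0.2 to 0.5. In the base case (7.6, 1.2, 0.3), 7.0% are called in remission on one value (range 3.3 to 15.7%). Of those, 57% have true HbA1c of 6.5% or more, so misclassification proper is 0.57 × 7.0 = 4.0%. Requiring two quarterly values below 6.5% gives 3.1% (1.5 to 7.2%).

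**6. Effect on the contrast.** Take 46% against 4% from Section 2.2 as an illustration. A false-call rate f among true non-remitters, equal by arm, gives p + (1 − p)f:

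| f | HIWL | DSME | Difference | Odds ratio | Power, 24 per arm |
|---|---|---|---|---|---|
| 0 | 46.0% | 4.0% | 42.0 | 20.4 | 94.5% |
| 5% | 48.7% | 8.8% | 39.9 | 9.8 | 88.9% |
| 10% | 51.4% | 13.6% | 37.8 | 6.7 | 81.9% |

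Unequal error biases. With true remission 4% in both groups and f assumed at 15% in HIWL against 5% in DSME, the rates are 18.4% and 8.8%, and 60 against 30 participants reject about 20% of the time at a nominal two-sided 5%.

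**7. Price of a two-value rule.** With error SD 0.3, a true 6.2% falls below 6.5% with probability Φ(0.3/0.3) = 84% on one value and 0.84² = 71% on two independent values.

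**The case against.** The strongest reply is that Section 4.1 already asks for 12 months, so the real defect is conflicting definitions, and reconciling them settles duration. The conflict is real and must be resolved. But the partial grade in 4.1 cannot be met in this trial, and settling on 8.1, the rule that can be applied, would leave the gap open.

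Three stronger readings are tempting, and the documents do not support them.

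- **That a large share of lowest-dose participants would be miscalled.** Letting people stop and restart repeatedly at 14-day reviews gives 7–26% at untreated 7.0% and 23–53% at 6.7%. Section 6.5.1 describes no such cycle: it permits discontinuation and, above 140, an increase, with no restart rule after a stop. Table 4 also allows drugs to be cut or stopped when weight loss begins, which favours early stops in HIWL.
- **That the whole-trial excess is several points.** This needs the share of participants untreated or on the lowest dose, which is not given. At an assumed 40% share and 7%, it is 2.8 points.
- **That noise manufactures a treatment effect.** Noise also removes true remissions and matters mainly near 6.5%. Randomisation balances regression to the mean, and equal error shrinks the contrast.

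Differential timing has a route in the text. Section 6.5.1 ties HIWL adjustments to the start, to encounters with hypoglycaemia and to quarterly HbA1c, but gives DSME weekly log review; HIWL + CGM has continuous data (8.2). The documents show neither that stop timing will differ nor in which direction.

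**Conclusion.** The point holds as a gap in a secondary endpoint. As written, Section 8.1 can count a recently stopped participant as in remission, and no other section prevents it. That follows from the text and needs no simulation.

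The size does rest on assumptions: HbA1c variability, lag, drug effect, the share untreated or on the lowest dose, and the timing of stops. Within the ranges shown, late stops probably account for a few per cent of lowest-dose participants. About 7% (3 to 16%) of unchanged, untreated entrants would be called in remission, a little over half of them with true HbA1c of 6.5% or more. The 6.5% entry floor on which the second figure depends appears only in the synopsis. The likely effect on H2b is dilution. Bias in either direction is possible but not shown. The primary weight analysis is untouched. The change is worth making because it is cheap.

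**What to change.** Reconcile Sections 1.1, 3, 4.1, 8.1 and 9.1 into one remission definition, and refer to it in 9.4.1. Suggested text:

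*A participant is in remission at 12 months if the month-12 HbA1c is below 6.5% and no anti-diabetes medication was taken from the month-9 medication review to the month-12 assessment. Remission is complete if that HbA1c is below 5.7%, otherwise partial.*

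Report two sensitivity analyses: the single-visit rule of 8.1, and a stricter rule requiring HbA1c below 6.5% at both month 9 and month 12. The two-value rule is the one that addresses unchanged, untreated entrants. Because it also loses true remissions (84% to 71% in the example above), it should not be the main definition.

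Add a rule for a missed month-9 medication review. For example, take drug status from the health-record and pharmacy sources named in 8.1, and classify as not in remission if it remains unknown.

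Cost: wording and one derived variable. HbA1c and medications are already planned quarterly (8.1), but the schedule in 1.3 shows medication review only at screening and must be aligned. This classifies an endpoint and changes no treatment. The downside is that genuine remissions whose drug stopped after month 9 are not counted, so reported rates will be somewhat lower.
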